## 13.2 Analysis Plan

### 13.2.1 Primary Endpoint

The analysis for both phase II and III component would be intention-to-treat (ITT), which means that all patients who signed a consent form and are randomized are included in the analysis and will be analyzed in the arms to which they are randomized.

#### Phase II component

**Final analysis:** The Phase II decision-making will be conducted when at least 191 events are observed (approximately expected 37 months after the first patient enrolled). If less than 191 events are observed 2 years after Phase II accrual ends, then the Phase II decision will occur at the target data lock.

At the final analysis of the Phase II, it will be concluded that the experimental arm regimen is promising, if we a one-sided p-value  $< 0.10$  from the log-rank test favoring the experimental arm.

*As of Amendment 04, there will be no additional accrual to the Phase III component of the trial regardless of the outcome of the Phase II analysis. Given the maturity of follow-up on the current patients and no additional accrual to the trial, the final Phase III OS analysis will also be performed at the time of final Phase II EFS analysis. All Phase III alpha (one-sided 2.5%) will be spent at this analysis. The target data lock date is August 12, 2024.*

**Interim analysis:** We will conduct a futility interim analysis which will take place after 50% of the total events have occurred (approximately 25 months after the first patient enrolled). If at the planned interim analysis the hazard ratio is  $>1.0$  in favor of the control arm, the recommendation will be to stop further accrual to the experimental arm and conclude that the novel regimen does not have improved EFS.

We will suspend accrual between phase II and III. In order to protect the phase III comparison, the results of the phase II portion will only be released to the FDA and/or industry sponsors for regulatory purposes, contingent upon the approval and recommendation from the Alliance Data Monitoring Committee. Other than that, the Alliance DMC will only release whether the criteria for continuation to Phase III have been satisfied and not any of the actual results.

#### Phase III component

The final analysis will be conducted after 521 deaths have been observed. In addition, we will conduct 2 interim analyses which will take place after approximately 50% and 75% of the total events have occurred. The first interim analysis is for futility only, and the second interim for both futility and efficacy. If in the second interim evaluation, sufficient evidence (per criteria outlined below) is observed that the experimental arm is superior to the control arm in terms of OS, then accrual to the control arm may be suspended and terminated. To preserve the Type I error rate control on superiority, the Lan-DeMets error spending function with the O'Brien-Fleming stopping boundaries is utilized. Futility boundaries

have also been developed for the comparison against control, where if at any of the planned interim analyses the hazard ratio is  $>1$  in favor of the control arm, the recommendation will be to stop further accrual to the experimental arm (if the trial is still accruing) and conclude that the novel regimen does not have improved OS. At the final analysis, if we observe a p-value  $\leq 0.022$  from the log-rank test (equivalently,  $HR \leq 0.838$  favoring the experimental regimen, assuming the exponential distribution) we will conclude that the novel regimen significantly improves the OS, compared to the daunorubicin and cytarabine arm. The interim and final analysis boundaries and characteristics were generated using the East clinical trial software program (version 6.3, Cytel Inc).

Information Fraction	Cum. events	Cum. alpha spent	Cum. beta spent	Efficacy Boundaries			Futility Boundaries	
				HR	P-value	Z score	HR	p-value
50%	261	0	0.01	NA	NA	NA	1	0.5
75%	391	0.010	0.011	0.789	0.010	-2.339	1	0.5
100%	521	0.025	0.1	0.838	0.022	-2.012	0.838	0.022

As of Amendment 04, there will be no additional accrual to the Phase III component of the trial regardless of the outcome of the Phase II analysis. Given the maturity of follow-up on the current patients and no additional accrual to the trial, the final Phase III OS analysis will also be performed at the time of final Phase II EFS analysis. The final Phase III of analysis of OS will conclude that the novel regimen significantly improves the OS compared to the daunorubicin and cytarabine arm if the one-sided p-value from the stratified log-rank test is  $< 0.025$ . The target data lock date is August 12, 2024.

### 13.2.2 Secondary Endpoints

- 1-year EFS rate:** The 1-year EFS rate is the proportion of efficacy evaluable patients event-free 1 year from registration. Patients who fail to achieve a CR/CRI during the induction, relapse, or die prior to 1 year after randomization/registration will be considered as a failure for this endpoint. Patients who are removed from protocol treatment for allogeneic HCT will continue to be followed for relapse or death at 1 year. Patients who are removed from study for other non-protocol therapy without relapse or CR/CRI during induction are also considered as a failure for the 1-year EFS endpoint.
- Disease-free survival (DFS):** DFS will be calculated as the time from achieving a CR/CRI to the time of relapse and/or death. Any patients who have not achieved the event of interest will be censored at the time of their last evaluation.
- Complete Remission (CR) and overall response rates:** Response to treatment will be assessed according to the Revised Recommendations of the International Working Group for Diagnosis, Standardization of Response Criteria, Treatment Outcomes, and Reporting Standards for Therapeutic Trials in Acute Myeloid Leukemia.
- Toxicity and tolerability:** As per NCI CTCAE v5.0, the term toxicity is defined as adverse events that are classified as either possibly, probably, or definitely related to the study treatment. The maximum grade for each type of toxicity will be recorded for each patient, and frequency tables will be reviewed to determine toxicity patterns. In addition, we will review all adverse event data that is graded as 3, 4, or 5 and classified as either “unrelated” or “unlikely to be related” to study treatment in the event of an

actual relationship developing. The incidence of severe (grade 3+) adverse events or toxicities will be described for each treatment arm, but will also be compared between the arms. Fisher's exact tests will be used to quantitatively compare the incidence of severe as well as specific toxicities of interest between the treatment arms and we will graphically assess differences in maximum grades observed for toxicities between the arms. Toxicity and tolerability will be monitored regularly. The study will be reviewable by the Alliance DSMB every 6 months to identify any toxicity or tolerability issues in either of the treatment arms.

- Association of clinical outcomes with pretreatment disease and patient characteristics. We will examine whether CR, EFS, DFS, and OS are predicted by pretreatment characteristics such as age, morphology, cytogenetics, immunophenotype, molecular genetic features, WBC count and hemogram, and performance status with clinical outcomes. The associations between these baseline factors and CR, EFS, DFS, and OS will be analyzed using Kaplan-Meier curves, log-rank test, contingency table and chi-square test whenever appropriate. Multivariable analysis including Cox proportional hazards models and logistic regression models will be used as well to evaluate the associations.

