## 9.0 ADVERSE EVENTS

The prompt reporting of adverse events is the responsibility of each investigator engaged in clinical research, as required by Federal Regulations. Adverse events must be described and graded using the terminology and grading categories defined in the NCI's Common Terminology Criteria for Adverse Events (CTCAE), Version 5.0. The CTCAE is available at [ctep.cancer.gov/protocolDevelopment/electronic\\_applications/ctc.htm](http://ctep.cancer.gov/protocolDevelopment/electronic_applications/ctc.htm). Attribution to protocol treatment for each adverse event must be determined by the investigator and reported on the required forms. Please refer the NCI Guidelines: Adverse Event Reporting Requirements for further details on AE reporting procedures.

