## 9.2 CTCAE Routine Reporting Requirements

In addition to the solicited adverse events listed in [Section 9.1](#), the following table outlines the combinations of time points, grades and attributions of AEs that require routine reporting to the Alliance Statistics and Data Center. Questions about routine reporting should be directed to the Data Manager.

Combinations of CTCAE Grade & Attribution Required for Routine AE Data Submission on Case Report Forms (CRFs)

Attribution	Grade 1	Grade 2	Grade 3	Grade 4	Grade 5
Unrelated			a	a	a
Unlikely			a	a	a
Possible		a	a, b	a, b	a, b
Probable		a	a, b	a, b	a, b
Definite		a	a, b	a, b	a, b

- a) Adverse Events: Other CRF - Applies to AEs occurring between registration and within 30 days of the patient's last treatment date, or as part of the Clinical Follow-Up Phase.
- b) Adverse Events: Late CRF - Applies to AEs occurring greater than 30 days after the patient's last treatment date.

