## **13.0 STATISTICAL CONSIDERATIONS**

### **13.1 Study Design**

This is an open-label, randomized phase II/III study.

The primary objective of the Phase II study is to determine based on the event-free survival (EFS) whether the combination of uproleselan plus daunorubicin/cytarabine should be tested further against standard of care: daunorubicin/cytarabine in the phase III component of this trial.

The primary objective of the Phase III study is to compare the OS between uproleselan plus daunorubicin/cytarabine versus the control arm (daunorubicin/cytarabine). Patients accrued during the Phase II portion of the trial will be used in the Phase III analysis.

Randomization: Randomization will be stratified on the following stratification factors: age (60-69 vs. 70 and older), performance status (0-1 vs. 2-4), de novo vs. secondary/therapy related AML. Patients will be randomized to receive one of the two treatment regimens with equal allocation using a permuted block method to balance the stratification factors.

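### Section 13.2.2 defines toxicity by investigator attribution in an open-label add-on trial and does not say which event set the between-arm safety tests use

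*Combined protocol and SAP*

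**What the plan says.** The toxicity and tolerability item of section 13.2.2 sets the definition: "the term toxicity is defined as adverse events that are classified as either possibly, probably, or definitely related to the study treatment". It then uses the term in four places.

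- **Tables:** "The maximum grade for each type of toxicity will be recorded for each patient, and frequency tables will be reviewed to determine toxicity patterns".
- **Grade 3+ incidence:** "severe (grade 3+) adverse events or toxicities will be described for each treatment arm, but will also be compared between the arms".
- **Tests:** Fisher's "exact tests will be used to quantitatively compare the incidence of severe as well as specific toxicities of interest between the treatment arms".
- **Graphs:** differences between arms in the maximum grade of toxicities are to be assessed visually.

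Grade 3-5 events rated unrelated or unlikely are to be reviewed, in case a relationship emerges. No analysis is named as the main one, and no alpha or sidedness is given for the Fisher tests.

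Three other parts of the protocol bear on this.

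- Section 13.1: "This is an open-label, randomized phase II/III study".
- Section 9.0: "Attribution to protocol treatment for each adverse event must be determined by the investigator".
- Sections 7.1 and 7.2: both arms receive daunorubicin and cytarabine, and Arm 2 adds uproleselan in induction and consolidation.

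**The concern.** Randomization protects a comparison of events. It does not protect a comparison of events filtered by a judgement made after randomization by someone who knows the arm. Here that judgement is relatedness to protocol treatment, and protocol treatment includes an extra investigational drug in one arm only. If the share of events called related differs by arm, the attributed rates differ even when the true rates are equal. The same filter can also mask a true difference.

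Two features add to this. The phrase covering both adverse events and toxicities leaves the tested set open, so the choice could be made after the data are seen, in what the protocol's cover page calls an FDA registration study. And under section 9.2, unsolicited grade 2 events are submitted only when rated at least possibly related, so attribution acts on the maximum-grade displays at collection as well as at analysis.

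What is at stake is the credibility of the between-arm safety statements, including oral mucositis, where sections 1.3 and 1.5 raise the prospect of a benefit from uproleselan.

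**Working it through.** **1. Which comparison uses which set.**

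| Item in 13.2.2 | Set, as worded |
|---|---|
| Maximum-grade tables | Attributed (toxicity) |
| Graphical maximum-grade comparison | Attributed (toxicity) |
| Fisher tests of specific toxicities of interest | Attributed (toxicity) |
| Grade 3+ incidence, described and compared | Either; not stated |
| Grade 3-5 unrelated or unlikely | Reviewed; no comparison named |

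**2. Which data exist regardless of attribution.** Section 9.2 requires grade 3-5 events at every attribution level through 30 days after last treatment. The late form takes only related events, so 30 days is the safe limit for an all-cause comparison. Section 9.1.2 solicits and grades seven terms, at baseline and each cycle, with no attribution condition: febrile neutropenia, nausea, diarrhea, oral mucositis, ALT, AST and bilirubin. Unsolicited grade 2 events rated unrelated or unlikely are not required, so they cannot be recovered later.

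**3. Size, as an illustration.** The plan gives no rate, power or alpha for these tests, so there is no stated figure to reproduce.

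Inputs:
- n = 131 per arm, from section 13.1.2. As a check on the design that supplies it, 191 events at HR 0.64 and one-sided 0.10 give Φ(√191/2 × 0.4463 − 1.2816) = Φ(1.802) = 0.964, against the stated 96%.
- Assumed: the same true event rate π in both arms (20%, 40%, 60%); attributed shares s_C (control) and s_E (experimental); two-sided Fisher test at 0.05.

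The attributed rates are π·s_C and π·s_E. For π = 40% and shares of 60% v 80%, they are 0.40 × 0.60 = 24% and 0.40 × 0.80 = 32%.

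The false-positive rate is the sum of Bin(i; 131, π·s_C) × Bin(j; 131, π·s_E) over all pairs (i, j) with Fisher p ≤ 0.05. It was calculated exactly, without simulation:

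| Shares, control v experimental | π = 20% | π = 40% | π = 60% |
|---|---|---|---|
| All events counted | 3.6% | 3.8% | 3.8% |
| 70% v 70% | 3.3% | 3.6% | 3.9% |
| 85% v 90% | 3.9% | 4.7% | 6.5% |
| 60% v 70% | 5.3% | 9.0% | 13.9% |
| 70% v 80% | 5.2% | 8.6% | 14.2% |
| 60% v 80% | 11.6% | 25.8% | 46.2% |
| 70% v 90% | 10.9% | 24.4% | 46.2% |

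Equal shares cause no inflation. Reversing the shares (80% v 60%) gives the same rates as 60% v 80%, but as a false advantage for the experimental arm. A true difference can also vanish: true rates of 30% v 40% with shares of 80% v 60% give 0.30 × 0.80 = 24% and 0.40 × 0.60 = 24%.

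**The case against.** A reader might infer that the arms are compared on attributed events alone. The documents do not support that. The grade 3+ sentence names adverse events alongside toxicities and says they will be compared. Because toxicity is defined by attribution in the same item, adverse events there reads naturally as the all-cause set. Secondary objective 2.2.3 is written in terms of adverse events. An all-cause grade 3+ comparison is thus permitted, and the data for it are collected. This objection stands, and it narrows the point to the unstated choice of set for grade 3+ and to the items worded only as toxicities.

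A reader might also infer that uproleselan would be made to look more toxic. That direction is not established. Attribution is to protocol treatment as a whole, which includes the same chemotherapy in both arms. Sections 1.3 and 1.5 lead investigators to expect less mucositis with uproleselan, and section 10.2 reports no safety concern to date. Either could lower attribution in the experimental arm.

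Third, the inflation may be small. The threshold is only a possible relationship, and sections 10.3 and 10.4 list myelosuppression and mucositis or stomatitis among the common reactions to the chemotherapy, with diarrhea and raised transaminases under cytarabine. Attribution could be high in both arms; at 85% v 90% little happens. This also stands: the documents give no attribution share by arm.

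Finally, the consequences are bounded. No decision rule hangs on the Fisher tests, the stopping rule in section 13.4 counts 30-day deaths whatever the cause, and the DSMB reviews toxicity twice a year.

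None of this says which set is tested for grade 3+, or gives an all-cause counterpart for the specific-toxicity tests and maximum-grade displays.

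**Conclusion.** The concern holds as a matter of specification. Section 13.2.2 ties the maximum-grade tables and displays and the specific-toxicity tests to investigator attribution, and leaves the grade 3+ test set unstated. In this design attribution may differ by arm, so comparisons made that way can create or hide a difference in either direction.

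For true rates of 20% to 60% and 131 per arm, the illustrative false-positive rate moves from about 4% (all events counted) to 3.9-6.5% at shares of 85% v 90%, and to 11.6-46.2% at 60% v 80%. The event rates, the shares and the two-sided 0.05 level are assumptions. The range shows what could happen and does not estimate what will.

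The change is worth making because it is cheap and the data exist. It concerns a secondary safety analysis and leaves EFS and OS untouched.

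**What to change.** Amend the toxicity and tolerability item of section 13.2.2, before the between-arm safety comparisons are run, to state that:

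1. The main between-arm Fisher tests and maximum-grade displays are all-cause. They use grade 3-5 events through 30 days after last treatment, and any grade for the seven solicited terms in section 9.1.2.
2. Events judged possibly, probably or definitely related are reported by arm as supportive and descriptive.
3. Any display of unsolicited grade 2 events is labelled as limited to those judged related, because unrelated ones are not collected.

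The cost is wording only, with no new data collection. The downside is that all-cause rates include disease-related events, which slightly dilutes a drug-specific signal; the supportive attributed summary keeps that information visible.

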The adverse events (AEs) observed in these AML patient populations were typical for induction chemotherapy and no specific uproleselan-related concerns have been identified. While most events were reported at similar rates as reported in the literature for MEC and 7+3, the incidence and severity of mucositis was low overall with only 2 Grade 3/4 events reported in 2 R/R subject treated with MEC (3%). These data suggest that uproleselan may reduce the incidence and severity of chemotherapy-induced mucositis, thereby providing an important safety advantage over chemotherapy alone.

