**Table 3      Oral Mucositis Adverse Events Reported During Induction in GMI-1271-201, N (%)**

Oral Mucositis Adverse Event	Phase I R/R (MEC)	Phase II R/R (MEC)	Total R/R (MEC)	RP2D R/R (MEC)	Older Adult Newly Diagnosed (7+3)
Evaluable Patients	19	47	66	54	25
Grades 1/2*	5 (26)	9 (19)	14 (21)	9 (17)	5 (20)
Grades 3/4*	1 (5)	1 (2)	2 (3)	2 (3)	0

\*AE grade definitions follow CTCAE v4.03.

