## 1.5 Rationale

We will conduct a randomized study testing the addition of uproleselan to a standard daunorubicin/cytarabine regimen in older adults with previously untreated AML. E-selectin inhibition with uproleselan in AML is attractive in that it targets both disease biology (adherence/activation of AML blasts) and a host response contributing to treatment morbidity (macrophage trafficking to the site of chemotherapy injury in the gut mucosa). The administration of uproleselan with chemotherapy in the initial Phase I/II study resulted in 1) higher than expected CR/CRi rates, 2) low induction-related mortality rates, and 3) low Grade 3/4 events of mucositis and warrants further investigation in a randomized study.

We propose a randomized phase II/III trial using EFS as the phase II endpoint and OS as the phase III endpoint. Although we are ultimately interested in agents that provide an overall survival benefit to patients, a shorter, intermediate endpoint is desirable to screen potential novel agents more quickly for phase III testing. In AML, the lack of surrogate endpoints that predict OS remains a major barrier for clinical development. There are several reasons for this including the availability of potentially effective salvage regimens including allogeneic HCT (alloHCT). The most common endpoint used in phase II AML studies are rates of morphologic CR. A drawback of the use of CR as a phase II endpoint in an upfront study is that it does not take into consideration the potential beneficial effects of the study agent in consolidation therapy. Another drawback to CR as an endpoint is that promising improvements in CR have later been demonstrated to show no benefit to overall survival as a result of increased toxicity and non-relapse mortality.

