Upon completion of AE entry in Medidata Rave, the CRA submits the AE for rules evaluation by completing the Expedited Reporting Evaluation form (i.e., checking the box *Send All AEs for Evaluation* and save the form). Both NCI and protocol-specific reporting rules evaluate the AEs submitted for expedited reporting. A report is initiated in CTEP-AERS using information entered in Medidata Rave for AEs that meet reporting requirements. The CRA completes the report by accessing CTEP-AERS via a direct link on the Medidata Rave Expedited Reporting Evaluation form. Contact the CTSU Help Desk at [name] or by email at [[contact]](mailto:[contact]) if you have any issues submitting an expedited report in CTEP-AERS.

In the rare occurrence that internet connectivity is lost, a 24-hour notification is to be made to CTEP by telephone at [contact]. Once internet connectivity is restored, the 24-hour notification that was phoned in must be entered immediately into CTEP-AERS using the direct link from Medidata Rave.

Additional information about the CTEP-AERS integration is available on the CTSU members' website:

- Study specific documents: Protocols > Documents > Protocol Related Documents > Adverse Event Reporting; and
- Additional resources: Resources > CTSU Operations Information > User Guides & Help Topics.

NCI requirements for SAE reporting are available on the CTEP website:

- NCI Guidelines for Investigators: Adverse Event Reporting Requirements is available at [https://ctep.cancer.gov/protocolDevelopment/electronic\\_applications/docs/aeguidelines.pdf](https://ctep.cancer.gov/protocolDevelopment/electronic_applications/docs/aeguidelines.pdf).

**9.1.2 Solicited Adverse Events:** The following adverse events are considered "expected" and their presence/absence should be solicited, and severity graded, at baseline and for each cycle of treatment by CTCAE, PRO-CTCAE, or both.

CTCAE v5.0 Term	CTCAE v5.0 System Organ Class (SOC)
-----------------	-------------------------------------

Febrile neutropenia	Blood and lymphatic system disorders
Nausea	Gastrointestinal disorders
Diarrhea	Gastrointestinal disorders
Oral mucositis	Gastrointestinal disorders
Alanine aminotransferase increased	Investigations
Aspartate aminotransferase increased	Investigations
Blood bilirubin increased	Investigations

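### Oral mucositis, one of three stated reasons for the trial, is not named in the toxicity analysis and its maximum grade is compared only by graph; a supportive ordinal comparison would add modest power (CONSIDER)

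*Combined protocol and SAP*

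**What the plan says.** - Section 1.3 states that "uproleselan may reduce the incidence and severity of chemotherapy-induced mucositis". Section 1.5 lists three results that led to this trial; the third is "low Grade 3/4 events of mucositis and warrants further investigation in a randomized study".
- Section 9.1.2 lists seven solicited events, oral mucositis among them, and says "their presence/absence should be solicited, and severity graded, at baseline and for each cycle of treatment by CTCAE, PRO-CTCAE, or both".
- Section 13.2.2 (Toxicity and tolerability) holds the graded variable: "The maximum grade for each type of toxicity will be recorded for each patient". It defines toxicity as events at least possibly related to treatment.
- For the between-arm comparison, section 13.2.2 says that Fisher's "exact tests will be used to quantitatively compare the incidence of severe as well as specific toxicities of interest between the treatment arms", and that "we will graphically assess differences in maximum grades observed for toxicities between the arms". Severe means grade 3 or higher. The toxicities of interest are not listed, and no grade cut is given for them.
- Section 13 does not mention mucositis and gives no ordinal test, significance level or power for any toxicity.

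**The concern.** The rationale covers both how often mucositis occurs and how severe it is. Severity is ordinal, and the grades are collected. The one comparison the plan assures cuts the scale at grade 3, where Table 3 shows few events with uproleselan: 0 of 25 older adults on 7+3 and 2 of 66 relapsed or refractory patients. Most recorded events were grade 1/2 (5 of 25 and 14 of 66). Accrual has closed, so the planned growth to 335 per arm will not happen. A reduction spread over all grades could be read as no difference in severe mucositis. Graphs would show the pattern but give no estimate or interval, and a test chosen after seeing them would be post hoc.

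**Working it through.** **Sample size.** The documents give no power for mucositis. The N used here is the planned 131 per arm from section 13.1.2. The EFS power stated for that N reproduces with 191 events, HR 0.64 and one-sided 10%: Φ(√191/2 × |ln 0.64| − 1.2816) = Φ(6.910 × 0.4463 − 1.2816) = Φ(1.802) = 96.4%, against 96% stated. The number actually randomised is not in the documents.

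**Uproleselan arm.** Table 3 pooled: grade 1/2 in 14 + 5 = 19 patients, grade 3/4 in 2 + 0 = 2, none in 91 − 21 = 70. That is 76.9 / 20.9 / 2.2%, taking the two rows as different patients.

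**Control arm (assumed).** A common odds ratio is applied at both cuts. For OR 2:
- any grade: odds 21/70 = 0.300, doubled to 0.600, so 0.600/1.600 = 37.5%
- grade 3+: odds 2/89 = 0.0225, doubled to 0.0449, so 0.0449/1.0449 = 4.3%

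The grade 3+ test then compares about 131 × 0.043 = 5.6 events with 131 × 0.022 = 2.9. The any-grade test compares about 49 with 30.

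**Power**, two-sided 5% (also assumed). Fisher is by full enumeration. Wilcoxon is tie-corrected and simulated on three levels (none, 1/2, 3/4). Distributions are percentages in that order, control v uproleselan.

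| Scenario | Fisher 3+ | Fisher any grade | Wilcoxon |
|---|---|---|---|
| No difference | 1% | 4% | 5% |
| OR 1.75 | 5% | 48% | 53% |
| OR 2 | 8% | 68% | 73% |
| OR 2.5 | 15% | 91% | 93% |
| 62/30/8 v 77/21/2 | 50% | 71% | 81% |
| 65/25/10 v 80/18/2 | 73% | 74% | 84% |
| Severe only: 77/13/10 v 77/21/2 | 73% | 4% | 6% |

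Leaving out the null and severe-only rows, Wilcoxon gains 11 to 78 points over Fisher on grade 3+ and about 2 to 10 over Fisher on any grade.

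**Other assumptions.** With grades 0 to 4, control any-grade rates of 20 to 60% (grade 3+ 3 to 15%) and a treatment odds ratio of 0.5, the ranges are 4 to 35%, 45 to 77% and 52 to 85%. Over those five scenarios the gain over any-grade Fisher is about 6 to 8 points. For a shift confined to the higher grades (control 60/12/16/10/2 v 60/27/11/2/0), Fisher on grade 3+ has 88%, Wilcoxon 20% and Fisher on any grade 4%.

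**The case against.** - **A second Fisher test is allowed.** Oral mucositis is an obvious candidate for an unlisted toxicity of interest, and an any-grade Fisher test comes within 2 to 10 points of Wilcoxon. This stands. What remains is that the test is permitted but not assured.
- **Section 1.5 speaks of Grade 3/4 events.** For that pattern the planned severe-grade test is much the better one. This also stands, so an ordinal test can only be an addition.
- **The objective is descriptive.** Objective 2.2.3 is to describe adverse events, and section 13.2.2 does so with frequency tables and graphs by arm. The plan is therefore not in error, and this lowers the priority.
- **The trial is open-label.** Under a common odds ratio most of the extra power comes from grade 1/2 events, the grades plausibly most open to assessor expectation. Any ordinal result needs that caveat.
- **The base rates are borrowed.** Of the 91 patients, 66 were relapsed or refractory on MEC, and the 25 older adults received idarubicin, not daunorubicin.

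A reader might infer that a true benefit would probably be reported as no difference. The documents do not support that: any-grade Fisher power is 48 to 91% in the common-odds-ratio scenarios, and the ordinal test itself misses about 47% of effects at OR 1.75. A reader might also infer that the question can be answered only in this trial; section 1.4 refers to other uproleselan trials in AML.

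**Conclusion.** The point holds as a modest improvement to a secondary safety analysis. A rationale-level outcome with graded data is unnamed in section 13.2.2, and the only test assured for it has about 5 to 15% power under common odds ratios of 1.75 to 2.5. The large shortfall applies only if no any-grade test is run. The ordinal test is not uniformly better and loses heavily when the effect is confined to severe grades. All sizes rest on assumed control rates, an assumed two-sided 5% level and 131 per arm. Priority: CONSIDER.

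**What to change.** In section 13.2.2:

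1. Name oral mucositis as a toxicity of interest.
2. Add a pre-specified supportive comparison of maximum CTCAE grade during induction, by a Wilcoxon rank-sum test stratified by the three randomisation factors (van Elteren), with a common odds ratio and 95% CI from a proportional-odds model.
3. Keep the grade 3+ Fisher test and show the by-grade table by arm, since one odds ratio cannot describe a severe-only shift.
4. State that the result is supportive, with no multiplicity-controlled claim, and that grade 1/2 assessment is open-label.
5. Count events regardless of attribution in this comparison, because attribution in an open-label trial can differ by arm. This departs from the section's definition of toxicity and should be stated.
6. Confirm that a CTCAE grade is held for every patient, since section 9.1.2 also allows PRO-CTCAE.

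Do not extend the method to unsolicited events, because section 9.2 does not collect grade 1 for them. The three factors give 2 × 2 × 2 = 8 strata; stratifying costs about 1 point of power. The change needs a few sentences and one analysis of data already planned for collection, with no new patients, visits or procedures. If mucositis has already been compared by arm, label the analysis post hoc.
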